9. STATISTICAL METHODOLOGY

9.1 General

Data listings will be provided for all data that is databased. Summary statistics and statistical analysis will only be presented for data where detailed in this SAP. For continuous data, summary statistics will include the arithmetic mean, arithmetic standard deviation, median, min, max, P25, P75 and N will also be presented. For categorical data, frequency count and percentages will be presented. Data listings will be provided for all subjects up to the point of withdrawal, with any subjects excluded from the relevant population highlighted. Summary statistics and statistical analyses will generally only be performed for subjects included in the relevant analysis population. For the calculation of summary statistics and statistical analysis, unrounded data will be used.

Data analysis will be performed using SAS® Version 9.4 or greater.

9.2 Demographics and Subject Disposition

Subject disposition will be listed. The demographic variables age, sex, race, ethnicity, type 1 diabetes mellitus and type 2 diabetes mellitus will be summarized and listed. All other demographic variables will be listed only. The demographic variables will also be compared, making the following comparisons:

- NG (Trained User) versus NG (Untrained User) – two sample t-test
- GEK (Trained User) versus GEK (Untrained User) – two sample t-test

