6.1. Inclusion Criteria

Participants are eligible for inclusion in the study only if they meet all of the following criteria at screening:

For all participants (Trained Users, PWDs and Untrained Users):

- [1] are at least 18 years old at the time of informed consent
- [2] are able to understand the purpose and procedure of the study and to give written informed consent to show their own willingness to participate in the study

Trained Users only:

- [3] are persons who are not diagnosed with T1DM or T2DM
- [4] are close friends/relatives of a patient who has been diagnosed with T1DM or T2DM and is being treated with insulin
- [5] have not previously administered any rescue medications (e.g. epinephrine, glucagon, narcan or seizure medications)
- [6] agree to not seek out information, or take any training, on how to administer either NG or injectable glucagon through the end of the study, except the training given as a part of the study

Untrained Users only:

- [7] have not been diagnosed with T1DM or T2DM, and are not a Trained User of a person with T1DM or T2DM
- [8] have not previously administered any rescue medications (e.g. epinephrine, glucagon, narcan or seizure medications); have not received training to administer any such medication; and agree not to take any such training through to the end of the study

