5.1 Types of Participants

Participants are defined as follows:

- **Trained User:** A participant who, during the study, will be given a level of training intended to mimic that of a real-life caregiver, relative, or close friend of a PWD.
 - “Trained User” participants must be either related to, or a close friend of, a PWD, and therefore already familiar with diabetes and the risk of severe hypoglycemia. Each Trained User must be recruited alongside the PWD with whom they are familiar, as a “dyad” (a pair of people who have a pre-existing relationship).
 - The Trained User will receive instruction on the use of each device, from the PWD, before taking part in the simulation using that device.
 - Trained Users must not have actually administered injectable glucagon (or another rescue medication) in the past. However, they may own a glucagon rescue kit, and may have been instructed in its use, as long as such instruction occurred at least 2 years before screening.
- **PWD:** The PWD who is the close friend or relative of the Trained User.
 - During the study, the PWD will be trained by site staff on the use of each device, and at least 7 days before each simulation, will relay these instructions to the Trained User.
 - The PWD previously may have been instructed in the use of a glucagon rescue kit, as long as such instruction occurred at least 2 years before screening.
- **Untrained User:** A participant who will not be given training during the study on either device, and who has limited knowledge of severe hypoglycemia and how to treat it.
 - These participants are intended to approximate a real-life colleague or acquaintance of a PWD: someone who is aware of the PWD’s condition and is willing to intervene in an episode of severe hypoglycemia, but has not received instructions. Untrained Users in this study may or may not know a PWD in real life. In any case, they must not have caregiving responsibilities toward a PWD.
 - Untrained Users will participate in the study alone (not as part of a dyad).
 - Prior to the simulations in this study, Untrained Users will be given basic information about severe hypoglycemia and briefly shown an example of each rescue device.

[Figure 1](#) (Part A) and [Figure 2](#) (Part B) illustrate the study design.

[figure not shown]
[figure not shown]

Figure 1 - Illustration of study design for Part A.

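### SAP 9.2 compares all demographic variables by two-sample t-test: for race with three or more categories the p-value depends on code order, and for T1DM/T2DM no meaningful test exists (minor)

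*SAP*

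**What the plan says.** SAP 9.2 (Demographics and Subject Disposition) first sets out the variables: "The demographic variables age, sex, race, ethnicity, type 1 diabetes mellitus and type 2 diabetes mellitus will be summarized and listed". It continues: "The demographic variables will also be compared, making the following comparisons". Two comparisons follow, each with its method: "NG (Trained User) versus NG (Untrained User) – two sample t-test" and "GEK (Trained User) versus GEK (Untrained User) – two sample t-test". No other method is given, and the sentence is not limited to continuous variables.

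The SAP offers no alternative test for these variables elsewhere. SAP 9.1 is purely descriptive on this: "For categorical data, frequency count and percentages will be presented". Protocol 10.3 likewise plans only descriptive summaries of baseline data, so the tests are an addition made in the SAP. SAP 11 nevertheless reports no change from the protocol's analyses.

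On diabetes status, Protocol 6.1 requires that Trained Users "are persons who are not diagnosed with T1DM or T2DM" (criterion 3) and that Untrained Users "have not been diagnosed with T1DM or T2DM, and are not a Trained User of a person with T1DM or T2DM" (criterion 7). Elsewhere in the SAP (Sections 6 and 9.4), diabetes type is that of the person with diabetes (PWD) who accompanies a Trained User. There is no such person in Part B: "Untrained Users will participate in the study alone (not as part of a dyad").

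**The concern.** A t-test compares means, so each variable needs a numeric scale. Age has one. A two-level variable such as sex can be coded 0/1 without harm. Nominal race with three or more categories cannot: the analyst must assign scores, the SAP fixes none, and the mean difference, its standard error and the p-value all depend on that choice.

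For T1DM and T2DM the difficulty is different. Under either reading of whose diabetes is meant, there is nothing to compare between the cohorts.

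The two cohorts are not randomized against each other. A reader may therefore take these p-values as evidence on whether Trained and Untrained Users are alike when looking at the between-cohort time comparisons and the exploratory GEE training effect in SAP 9.5. That is the extent of what is at stake.

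**Working it through.** SAP 9.2 states no figure to reproduce. The plan's only design figure, 90% power, is unaffected and reproduces: with n = 26, difference 0.40 and discordance 0.45, (0.40√26 − 1.96√0.45)/√(0.45 − 0.16) = 1.35, which gives power 0.911.

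**Inputs.** There are 26 participants per cohort (SAP 7). Race categories and counts are not in the documents. Three categories A, B and C are assumed, with illustrative counts 16/8/2 (Trained) and 16/3/7 (Untrained).

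**Race, one table.** The pooled t-test is t = (m₁ − m₂)/√(s²·2/26), with s² = (SS₁ + SS₂)/50 on 50 degrees of freedom. Reversing the codes 1-2-3 changes only the sign of t, so three distinct codings remain, set by which category takes the middle code.

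| Middle code | m₁ | m₂ | SS₁ + SS₂ | t | p |
|---|---|---|---|---|---|
| B | 38/26 | 43/26 | 30.35 | −0.89 | 0.378 |
| C | 44/26 | 39/26 | 34.04 | 0.84 | 0.405 |
| A | 46/26 | 56/26 | 18.00 | −2.31 | 0.025 |

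Pearson chi-square on the same table has expected counts 16, 5.5 and 4.5 in each cohort. It equals 2(2.5²/5.5) + 2(2.5²/4.5) = 5.05 on 2 degrees of freedom, p = 0.080, whatever the order.

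**Race, range of assumptions.** For each of six assumed mixes, 100,000 pairs of 26 v 26 were drawn with both cohorts from the same mix, and all three codings were applied.

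| Mix (%) | Median of largest minus smallest p | Codings disagree on p < 0.05 |
|---|---|---|
| 33/33/33 | 0.446 | 12.5% |
| 50/30/20 | 0.434 | 12.1% |
| 60/30/10 | 0.434 | 11.3% |
| 70/20/10 | 0.438 | 11.6% |
| 80/15/5 | 0.400 | 9.7% |
| 90/7/3 | 0.335 | 8.0% |

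Any single coding fixed in advance rejected in 3.5% to 5.2% of tables. The fault is dependence on coding, not an inflated error rate.

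**T1DM/T2DM.** There are three possible codings:

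- *Users' own diagnosis.* Criteria 3 and 7 give 0/26 v 0/26. Both variances are zero, so t = 0/0 and the test is undefined.
- *The PWD's type.* Part A has 26 values (13 of each type by recruitment, SAP 7) and Part B has none, so there is no statistic.
- *The PWD's type with Part B set to zero*, which nothing in the documents plans. For 13/26 v 0/26 the mean difference is 0.5, s² = 6.5/50 = 0.13, the standard error is √(0.13·2/26) = 0.10, t = 5.0 and p = 0.000007. This only restates the recruitment quota.

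**Two-level variables.** For 8/26 v 2/26 the t-test and the uncorrected chi-square both give p = 0.035; for 6/26 v 1/26 they give 0.043 and 0.042. No objection arises for sex, or for race and ethnicity if analysed in two categories.

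**NG and GEK versions (side note).** If everyone does both simulations, the two listed comparisons involve the same people and are the same test. With 1, 2 or 3 extra people per cohort in only one of them, the two t statistics correlate at about 0.98, 0.96 and 0.95. In the extreme case of 39 and 33 enrolled, with every non-completer doing one simulation, the correlation is about 0.84 to 0.85. The split is valid for age but redundant.

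**The case against.** The best defence is that a sensible programmer would use the t-test only where a mean exists, which is age. SAP 9.1 separates continuous from categorical summaries, and no one has planned to score race numerically. The table shells mentioned in SAP 3 were not available and may say exactly this. For T1DM/T2DM the likely result is an empty cell, not a misleading number, and SAP 13.3 says how to present tables without enough data. The illustrative race table also comes from the minority of tables in which the codings disagree about p < 0.05.

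Part of this stands. The race consequence is conditional on three or more categories and on someone applying the rule literally. The example shows the mechanism and is not a typical table. The defence does not remove the point, however. The limit to age is not in the SAP, which applies the t-test to a group of variables it has just listed. SAP 9.1 says which categorical summaries to give but supplies no other test. SAP 13.3 governs how an empty table looks and does not make an inapplicable comparison meaningful.

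**Conclusion.** The concern holds: the rule in SAP 9.2 is wrong as written for race and for T1DM/T2DM. The T1DM/T2DM part needs no assumed counts, only the eligibility criteria and the absence of a PWD in Part B. The race part assumes at least three nominal categories. Under the mixes examined, code order alone typically moves the p-value by about 0.34 to 0.45 and changes the call at 0.05 in 8% to 12.5% of tables.

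Severity is minor. Descriptive summaries are planned in any case, no model or decision uses these p-values, and the primary and first secondary comparisons are made within a cohort. The conclusion concerns the SAP wording; the table shells could already contain the restriction.

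**What to change.** In SAP 9.2:

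- Restrict the two-sample t-test to age.
- For sex, race and ethnicity, name chi-square or Fisher's exact test, or drop testing and describe only.
- Summarize diabetes type within Part A without a test, labelled as the PWD's type.
- Replace the separate NG and GEK versions with one Trained versus Untrained comparison per user-level variable.
- Optionally, record in SAP 11 that baseline tests were added to the protocol's descriptive plan.

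The cost is a few lines of wording and fewer tables. Data collection, sample size and the primary analysis are untouched.

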9.3 Adverse Events

Where changes in severity are recorded in the Case Report Form (CRF), each separate severity of the adverse event (AE) will be reported in the listings, only the most severe will be used in the summary tables. A pre-existing condition is defined as an AE that starts before the subject has provided written informed consent and is ongoing at consent. A non-treatment emergent AE is defined as an AE which starts after informed consent but prior to dosing. A treatment-emergent AE is defined as an AE which occurs postdose or which is present prior to dosing and becomes more severe postdose.

All AEs will be listed. Treatment-emergent AEs will be summarized by treatment, severity and relationship to the study drug. The frequency (the number of AEs, the number of subjects experiencing an AE and the percentage of subjects experiencing an AE) of treatment-emergent AEs will be summarized by treatment, Medical Dictionary for Regulatory Activities (MedDRA) version 21.0 system organ class and preferred term. The summary and frequency AE tables will be presented for all causalities and those considered related to the study drug. Any serious AEs will be listed.

Associated person AE's will be listed and summarized by treatment, severity and relationship to the study drug.

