3. INTRODUCTION

This SAP has been developed after review of the Clinical Study Protocol (final version dated 21 September 2018).

This SAP describes the planned analysis of the efficacy and safety data from this study. A detailed description of the planned TFLs to be presented in the clinical study report (CSR) is provided in the accompanying TFL shell document.

The intent of this document is to provide guidance for the statistical analysis of data. In general, the analyses are based on information from the protocol, unless they have been modified by agreement between Eli Lilly and Company and Covance Early Clinical (EC) Biometrics. A limited amount of information concerning this study (e.g., objectives, study design) is given to help the reader's interpretation. This SAP must be signed off prior to first subject simulation for this study. When the SAP and TFL shells are agreed upon and finalized, they will serve as the template for this study's CSR.

This SAP supersedes the statistical considerations identified in the protocol; where considerations are substantially different, they will be so identified. If additional analyses are required to supplement the planned analyses described in this SAP, they may be performed and will be identified in the CSR. Any substantial deviations from this SAP will be agreed upon between Eli Lilly and Company and Covance EC Biometrics and identified in the CSR. Any minor deviations from the TFLs may not be documented in the CSR.

This SAP is written with consideration of the recommendations outlined in the International Conference on Harmonisation (ICH) E9 Guideline entitled Guidance for Industry: Statistical Principles for Clinical Trials¹ and the ICH E3 Guideline entitled Guidance for Industry: Structure and Content of Clinical Study Reports².

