9.6 Other Assessments

All other assessments not detailed in previous sections will be listed but not summarized or statistically analyzed.

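### SAP 9.3 ties user AE tables to 'postdose' onset and 'study drug' relatedness in a study that doses no one, so a needle-stick before the GEK injection can be tabulated or only listed depending on device order

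*SAP*

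**What the plan says.** SAP 9.3 (Adverse Events) gives two definitions that share one anchor. The emergent class is: "A treatment-emergent AE is defined as an AE which occurs postdose or which is present prior to dosing and becomes more severe postdose". Its complement is: "A non-treatment emergent AE is defined as an AE which starts after informed consent but prior to dosing". All AEs, and any serious AEs, are listed. For users, the tables are confined to the emergent class: "Treatment-emergent AEs will be summarized by treatment, severity and relationship to the study drug". The relatedness split is also stated in terms of drug: "The summary and frequency AE tables will be presented for all causalities and those considered related to the study drug". AEs in associated persons, which I take to be the accompanying people with diabetes (PWDs), "will be listed and summarized by treatment, severity and relationship to the study drug". That sentence has no emergent restriction.

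Two general rules leave the remaining AEs without a planned table. SAP 9.1: "Summary statistics and statistical analysis will only be presented for data where detailed in this SAP". SAP 9.6: "All other assessments not detailed in previous sections will be listed but not summarized or statistically analyzed". SAP 3 adds that a detailed description of the planned outputs "is provided in the accompanying TFL shell document", which is not among the documents reviewed.

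Protocol 3.3 and 7.1 state that nobody receives drug as part of the study. Protocol 7.1.1 says the NG devices are supplied without drug product. Protocol 9.2 has the investigator document whether an AE may be related to treatment, device or procedure.

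**The concern.** The wording of SAP 9.3 suits a trial in which participants take a drug. Here they operate a device on a manikin. The one safety risk the protocol names is a needle-stick with GEK (Protocol 3.3, 9.2 and 9.4). An injury of that kind can happen before anything has been delivered to the manikin, and the emergent definition excludes events before delivery unless they worsen afterwards.

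At stake are the by-device counts and percentages of the one AE the study expects. If the same injury is counted or left out according to which device the user was randomized to use first, the GEK column does not describe GEK use. In the 'related' tables, an injury caused by a needle, and so by the device or the procedure, may not count as related to a drug.

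**Working it through.** No sample size or power figure enters, so the check applies the SAP definitions to one defined event.

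**Step 1: what a dose is.** The AE section does not define dosing. Elsewhere the usage points to the manikin. Protocol 5.1.2 asks whether users can administer a successful dose. Protocol 5.1.3.4 defines a complete dose by the position of the NG plunger, or by at least 90% of the GEK solution being given. I therefore read dosing as delivery to the manikin.

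**Step 2: when the needle is in use.** The GEK critical steps in Protocol 5.1.3.4 run: unpack, inject diluent into the vial, dissolve, draw up, inject the manikin. The syringe is handled for diluent and for draw-up before any delivery.

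**Step 3: classify the event.** Take a user's needle-stick while drawing up GEK in the simulation, with no later worsening. Table IGBM.2 (Protocol 7.2) has two orders.

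| Order | Delivered to a manikin before the injury | Class under SAP 9.3 | Output |
|---|---|---|---|
| GEK first (Schedule I) | Nothing | Non-emergent | Listing only |
| NG first (Schedule II), NG delivered at Simulation 1 | NG | Emergent | Listing and tables |
| NG first, NG not delivered at Simulation 1 | Nothing | Non-emergent | Listing only |

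The first two rows describe the same injury with the same device. Only the randomized order differs. If the first-row injury became more severe after a later delivery, the worsening clause would move it into the tables.

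**Step 4: is there another table for it?** No. SAP 9.1 and 9.6 default to listing, and SAP 9.3 plans no table of non-emergent AEs. SAP 3 permits additional analyses, but does not plan this one.

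**Step 5: relatedness.** Protocol 9.2 gives the investigator three possible causes: treatment, device and procedure. The SAP's 'related' tables use one, study drug. An injury judged related only to device or procedure can therefore be missing from those tables. If it is emergent, it stays in the all-causality tables. For NG the term fits poorly in any case, because the devices hold no drug. The same wording governs associated persons, who are not subject to the emergent filter.

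**Step 6: size.** The documents give no needle-stick rate, no allocation ratio and no split of injuries before and after injection. The affected share cannot be computed. If allocation were 1:1 (an assumption), 26 / 2 = 13 users in each cohort would have GEK first and fall under the first row. That counts users exposed to the rule, not injuries.

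**The case against.** The best defence is that this is carried-over wording which any programmer would interpret sensibly, for instance by taking the start of the simulation as dosing. On that reading the injury is tabulated in both orders. SAP 7 speaks of successful dosing, which could be taken to include an attempt. SAP 6 names NG and GEK as the study treatments, so study drug may simply mean study treatment. With 26 users planned per cohort, every needle-stick can be read from the listing. Protocol 10.3 summarizes safety only if event frequency allows. The table shells may already settle the derivation.

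Much of this stands, and it is why the point is minor. It does not remove the point, because the text as written gives a rule and the documents' own use of dose makes that rule depend on order. SAP 3 requires sign-off before the first simulation, and the study is open-label. If the anchor stays open, it may be settled once AEs are known.

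A reader might infer three stronger claims that the documents do not support:

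- *Needle-sticks would be missing from the user tables in both orders, because no human is dosed.* This needs dosing to mean a dose to a person. It would leave the planned tables empty except after an accidental injection of the comparator, which Protocol 3.3 allows for. That is a strained reading, given how the documents use the word.
- *User injuries in Part A training are systematically lost.* Protocol 5.1.3.1 has the PWD actuate the device and then pass on instructions. No section says the Trained User handles a device in training. PWD events carry no emergent filter, and a user event that worsened after delivery would be emergent.
- *A known fraction of injuries drops out.* Counting readings, steps or visits does not give one.

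**Conclusion.** The point holds as a minor one. Under the reading the documents best support, a GEK-first user's needle-stick before injection is listed but not tabulated unless it later worsens, while the same injury after NG delivery is tabulated. Separately, an injury judged related only to device or procedure can be absent from the 'related' tables.

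The effect is confined to descriptive safety tables. Nothing is lost from the listings, SAP 4 has no safety objective, and the primary comparison is unaffected. The conclusion assumes that dosing means delivery to the manikin and that the unseen table shells contain no overriding rule.

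**What to change.** In SAP 9.3, define an emergent AE as one that starts or worsens at or after the start of the participant's first device training session or simulation, whichever comes first. For Untrained Users this is the first simulation. The draw-up injury is then tabulated in both orders. Replace relation to study drug with relation to study treatment, study device or study procedure, for users and associated persons alike. If the table shells already hold an anchor, reconcile it with this text and state it in the SAP.

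The cost is a small change to SAP wording and table derivation. Protocol 9.2 already asks the investigator for the wider relatedness judgement. One consequence to accept is that in Part A, AEs arising in the roughly 7 days between Visit 1 training and the Visit 2 simulation become emergent, so the all-causality tables may include some events that have nothing to do with a device.
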